#### **Brief Summary:**

The goal of this study is to learn about supporting pregnant and postpartum women living with HIV with treatment adherence. The investigators will conduct a pilot study of an intervention that includes peer counseling about viral load levels and rapid delivery of viral load results. The investigators will evaluate the feasibility of the intervention, and will assess whether it improves viral suppression 6 months following the intervention, compared to historical controls.

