### 2) Rapid return of viral load results:

Mentor mothers will be trained to return viral load results to patients with scripted messaging according to viral load level (undetectable, low-level viremia (50-1000), high viral load (>1000)). Patients will be offered a choice of the mode of delivery, including text, phone, or in-person. Detectable viral loads will not be delivered by text, and women with high viral loads may be asked to return to the clinic for in-person counselling.

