### 3) Enhanced viral load counselling

Mentor mothers will reinforce adherence with all patients with undetectable levels via scripted messaging to reward and encourage healthy behavior. For those with any detectable levels, mentor mothers will be trained to provide targeted counseling about low-level and higher viral loads. Women who report significant psychosocial barriers will be referred to a social worker.

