### HIV care outcomes.

The viral loads collected as part of the intervention will guide the counselling that is provided during the study. Study outcome viral loads will be routine care viral loads that are collected (1) within the 6 months following the control participants enrollment (and only) study visit, for prospectively enrolled controls, (2) within the 6 months prior to the pilot study for controls

retrieved from electronic records, and (3) within the 6 months following the pilot participants last study visit. The study team will work together with the clinical teams to ensure these viral load outcomes are measured and recorded according to national guidelines. Viremia will be defined as any detectable levels of HIV RNA. Suboptimal care engagement will be defined as late for a clinic visit by 30 days or more.

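### Outcome viremia is any detectable HIV RNA on routine tests with no fixed copies/mL cut-off, so a change in reporting limit between periods could not be told apart from the intervention

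*Combined protocol and SAP*

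**What the plan says.** Section 3, under HIV care outcomes, gives the definition: "Viremia will be defined as any detectable levels of HIV RNA". No number is attached. The same paragraph sets the source: "Study outcome viral loads will be routine care viral loads that are collected" in a window that depends on the group.

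- Records controls: "within the 6 months prior to the pilot study for controls" taken from electronic records.
- Prospective controls: the 6 months after their single study visit, which takes place before the pilot.
- Pilot participants: "within the 6 months following the pilot participants last study visit".

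The team is to work with the clinics to "ensure these viral load outcomes are measured and recorded according to national guidelines". That sets a standard of practice but names no assay, platform or limit.

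The Xpert assay in Section 3(d) is for study samples. The outcomes paragraph separates the intervention viral loads, which guide counselling, from the outcome viral loads.

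The Brief Summary asks whether the intervention "improves viral suppression 6 months following the intervention", again without a threshold. Section 4 compares viremia by logistic regression adjusted for baseline clinical and demographic differences. Assay and reporting limit are not mentioned.

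**The concern.** Detectable is not a fixed quantity. The same blood level can count as viremic on a test that reports to a low limit and as non-viremic on one that reports to a higher limit. Within one laboratory and one period this would only blur the endpoint. Here the groups are compared across periods, at 2-4 clinics, on tests the study does not run.

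If the limit changed between the control and pilot windows, the change would line up with exposure. Where limit and period coincide completely, no baseline covariate can separate the limit from the intervention, so the Section 4 adjustment does not help. Results near the limit also matter more than usual here, because low-level viremia is the study's focus.

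At stake is the estimate of potential impact that is meant to inform later research. Unlike real change over time, this source of error can be removed by a definition.

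**Working it through.** **No figure to reproduce.** The documents give no expected viremia rate, effect size, power or sample-size calculation, and no routine reporting limits. What follows is for scale only.

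**Inputs from the documents.** Pilot group 275 (Detailed Description). Controls 125 + 150 = 275 (Detailed Description), or up to 125 + 320 = 445 (Section 3).

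**Assumptions not in the documents.** Viremia p = 10% or 20% at the higher limit. A further share s of women, 2-10%, have values between the two limits. True viral loads have the same distribution in all groups, so there is no real effect.

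**Step 1, do the windows overlap?** The records-control window ends when the pilot starts, so it cannot overlap any pilot outcome window. The prospective-control window starts before the pilot and, with no dates given, may partly overlap. The exposure is therefore clearest for the records controls.

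**Step 2, spurious difference.** A group read at the lower limit shows p + s and a group read at the higher limit shows p.

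- All controls differ from all pilot women: difference = s, which is 3-10 points for s of 3-10%.
- Only the 150 records controls differ: difference = s × 150/275 = 0.55s, which is 1.6-5.5 points.
- Only the records controls differ, and there are 320 of them: s × 320/445 = 0.72s, which is 2.2-7.2 points.

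**Step 3, sampling error for comparison.** At 20% viremia, SE = √(0.2 × 0.8 × 2/275) = 3.41 points. With 445 controls, SE = √(0.16 × (1/275 + 1/445)) = 3.07 points.

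**Step 4, odds ratios and rejection rates.** Unadjusted two-proportion test, two-sided 0.05, 275 versus 275, lower limit in the controls, no true effect:

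| p | s | All controls differ: OR (rejection) | Only 150 records controls differ: OR (rejection) |
|---|---|---|---|
| 10% | 2% | 0.81 (11%) | 0.89 (6%) |
| 10% | 5% | 0.63 (43%) | 0.76 (17%) |
| 10% | 10% | 0.44 (91%) | 0.61 (48%) |
| 20% | 2% | 0.89 (8%) | 0.94 (5%) |
| 20% | 5% | 0.75 (29%) | 0.85 (12%) |
| 20% | 10% | 0.58 (77%) | 0.73 (33%) |

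Example, p = 20%, s = 5%, all controls: (0.20/0.80) ÷ (0.25/0.75) = 0.75. If the pilot group had the lower limit instead, the ratio inverts to 1.33 and the intervention looks harmful.

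**Step 5, after the fix.** With one threshold no lower than the highest reporting limit in use, the difference due to the limit is zero by construction.

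**Step 6, cost in events.** With 20% viremic at the higher limit and 3-10% between limits, a cut-off at the higher limit drops 3/23 = 13% to 10/30 = 33% of the events that the more sensitive test would count.

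**The case against.** The strongest reply is that the harm is hypothetical. Nothing in the documents says that routine assays or limits differed by site or changed over time. A reader might infer that the comparison is already biased in the intervention's favour. The documents support neither the presence nor the direction of a bias. This stands, and it limits the point to what the definition permits.

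Second, one standard, the national guidelines, governs measurement for all groups. That is partly reassuring, but it fixes no limit. It is also true that differences between sites bias the comparison only if the site mix differs between groups. The prospective controls come from the pilot sites, so site differences should largely cancel for them. A change over time would not.

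Third, Section 3 states that the pre-post comparison is not causal, because time trends or other causes could explain a difference. That lowers the stakes, but it neither defines the endpoint nor excuses an avoidable artefact.

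Fourth, a reader might infer that the protocol carries several competing outcome definitions. It does not. The limit of 100 copies/mL or less in Section 1 is the rationale for a sensitive monitoring assay. The bands in Section 3(d), component 2 (undetectable, 50-1000, above 1000) sort counselling messages. Component 3 ("For those with any detectable levels, mentor mothers will be trained to provide targeted counseling") uses the same notion of detectable as the outcome. There is one real gap: a detected result below 50 has no band in component 2 yet triggers counselling under component 3. That concerns the scripts, not the outcome.

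**Conclusion.** The point holds as a conditional weakness in the endpoint definition. The stated rule lets the outcome follow the reporting limit of each routine test, and the planned analysis could not separate a limit change that tracks period from the intervention. Its size cannot be derived from the documents. Under the assumed s of 3-10%, it runs from under half a standard error (1.6/3.4, only the 150 records controls affected) to nearly three (10/3.4, all controls affected), in either direction. If the limits were the same throughout, it is zero. The change should be made because it is cheap and removes the problem, but the point does not undermine the pilot's feasibility aims.

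**What to change.** In Section 3, HIV care outcomes, define outcome viremia as HIV RNA at or above one stated copies/mL threshold, applied identically to all three groups. The plan's own boundary of 50 is a natural choice if every routine assay reports to that level. Otherwise, use the highest routine reporting limit in use in any window. Settle the value before outcomes are compared, and count results reported only as below that value as non-viremic.

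- Abstract the numeric result and, where available, the assay and its limit. Request these fields in the first records extraction, because de-identified data may be hard to supplement later.
- Report viral load above 1000 copies/mL and any-detectable as additional analyses.
- Use the same threshold for viral suppression in the Brief Summary.
- Separately, reconcile components 2 and 3 of Section 3(d) on detected results below 50.

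**Cost.** Protocol wording and a few abstracted fields, which the records may not hold. If the common limit is well above the lowest one, the primary definition loses events (13-33% in the illustration) and part of the low-level viremia the study targets. The any-detectable analysis keeps that information in view.

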#### Implementation outcomes.

Enola Proctor has proposed a taxonomy of implementation outcomes to inform systematic and scientifically rigorous measurement of implementation success. The pilot study outcomes summarized in Table 1 are outcomes which Proctor has identified as most salient to the early stages of implementation, while gaining training in the measurement of later stage outcomes to incorporate in my future research.

**Table 1. Implementation outcomes and method of measurement in the pilot study**

Outcome	Method of measurement	When measured
Acceptability (provider satisfaction, facilitators, barriers)	• Survey	End of pilot
Adoption (uptake, intention)	
 
Record for each enrolled participant
 
1. whether the viral load monitoring was conducted on schedule
 
2. what action was taken in response to low-level viremia
 
3. reasons for no action
 
	Daily throughout follow-up
Appropriateness (perceived fit)	• Survey	End of pilot
Feasibility (practicability, utility)	• Survey	End of pilot

The PIs and research team will lead training sessions for mentor mothers and research assistants prior to the start of the study, followed by periodic (at least monthly) follow-up sessions to reinforce initial plans and revise strategies as needed. These data will be entered into de-identified REDCap databases containing only anonymous study IDs. A separate secure list linking study IDs to clinic IDs will be maintained in order to later link these records to virologic outcomes. At the conclusion of the study, surveys will be administered to key stakeholders and care providers at the sites (n=~10) to measure acceptability and feasibility, and semi-structured in-depth interviews will be conducted to further assess acceptability, appropriateness and intentions. Interview guides will be informed by a rapid analysis of survey data and assessments of adoption.

Evaluating the potential impact on maternal viremia. We acknowledge that this pre-post analysis will not reflect a causal effect of the pilot on viremia risk, as any observed differences could be due to temporal or other factors. This pilot study, rather, aims to explore the *potential impact* while gathering critical data on the feasibility and acceptability of the intervention to inform future research.

#### **4. DATA MANAGEMENT**

Analyses of implementation outcomes. Analyses will summarize acceptability and feasibility survey results, summaries of adoption, as well as the clinical and sociodemographic characteristics of the women seen at the clinic during the pilot study, using descriptive statistics.

Evaluating the potential impact on maternal viremia. The frequency of viremia in the year preceding the pilot to the frequency among women seeking care during the pilot will be

compared with logistic regression, adjusted for baseline differences in clinical and demographic characteristics.

## 5. ETHICAL CONSIDERATIONS

Study databases will only include anonymous study IDs. In order to link baseline patient characteristics to viral load outcomes, we will maintain a separate secure list linking study IDs to clinic IDs. Only the PI and research team will have access to this linked ID list, and will use it to ensure data quality.

Potential risks will be minimal, and could include 1) discomfort having additional blood draws for additional viral load testing, and 2) loss of privacy or social harms due to loss of privacy.

Informed consent: We will obtain written informed consent from all women participating. Clinical care remains at the discretion of the treating clinician. The informed consent forms will describe the purpose of the study, the types of activities that will be conducted, and the risks and benefits of participation.

**Protections Against Risk:** Every effort will be made to ensure the privacy of participants. All study paper and study databases will only include de-identified data and study IDs. Lists matching study IDs to clinic IDs and provider names will be maintained in a separate REDCap project only accessible to the PI and the research assistant. Recording devices and paper informed consent forms, interview and observation notes, and any other paper materials containing human subject data will be stored in a locked file cabinet in a locked room. Audio recordings and interview transcripts will be stored in secure, password-protected, MyResearch online storage space to allow access in Kenya and San Francisco. MyResearch is supported in a secure, professional data center, locked and guarded 24x7 with UCSF badge access required for physical entry. Data exists on a private network with its own firewall. REDCap is housed in a locked and guarded data center. Entrance to the data center requires triple factor authentication: use of a card key to unlock the data center door, biometric authentication and a second card key lock secures the cage that the servers reside within. The security of the data center is monitored by a security camera system. REDCap servers are guarded by multiple firewall and intrusion detection systems. All electronic connections to the REDCap environment are encrypted.

